## THE STUDY HAS TWO PARTS:

PHASE 1. Is in progress and is setting up the feasibility trial. Phase 1 has approval from the University of Stirling Research Ethics Committee.

PHASE 2. We will study whether it is acceptable and possible to randomise obese men (like tossing a coin) to three groups: texts only; texts and incentive; or to a 'control group' who wait a year and then get the texts for 3 months. We will assess the feasibility of recruiting 105 obese men from two regions of Scotland. Half of the men will get an invitation letter from their GP. The other half will be approached in the community, given information about the study and invited to take part. Men can take part if their trouser waist is 40 inches and more or their Body Mass Index is 30 or higher. We want to find out how long it takes to find 105 obese men who want to take part, how many come back to suitable venues at 3, 6 and 12 months to get weighed and answer questions about their quality of life, lifestyle and motivation. We will try to include men from all walks of life, so we will ask questions at the start like their age, address, who they live with, or if they have any illnesses like diabetes. At the end we will ask men about their experiences and men from the control group will receive texts for 3 months if they wish. Control group texts will be developed based on the feedback and qualitative interview data received from the men in the two intervention groups at 3 months. In order to improve the acceptability of the texts to more men, these texts will be a different style from the original narrative texts. Drop-outs from the control group at 12 months will be replaced through recruiting further men until we have a sample of at least 30 men receiving the alternative texts. We will interview approximately 18-30 men in more detail about their experiences of weight loss and of being in the study. We will follow up all men from the alternative text group for 3 months, seek their feedback on the texts and interview 10-16 men in more depth about their experience. A PhD student will find out if it is possible to follow up the men for another year, and ask them questions on whether it is acceptable and possible to link the study findings to their health records.

Protocol, Game of Stones. V3, 14/02/2018

THE STUDY WILL TELL US if our approach is acceptable, possible to deliver and if it could help men to lose weight. If it is, then we will do a larger study.

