## Main research questions:

- 1. Are adapted narrative SMS interventions with embedded BCTs, with or without endowment incentives, acceptable and feasible to deliver in a RCT?
- 2. How can intervention components and outcome measurement procedures be optimised to increase reach, engagement and follow-up of obese men?
- 3. Are alternative SMS based on mixed method data analysis more acceptable and likely to improve trial retention at 3 months than the existing text message intervention?
- 4. Are progression criteria met for a full RCT for one or both interventions?
- 5. What are the likely recruitment and attrition rates?
- 6. What would be the sample size for a full trial of weight loss outcomes at 12 months?
- 7. How do the two interventions (SMS with and without endowment incentives) compare for health equalities, reach, engagement and retention?
- 8. Is data-linkage to long-term health and resource outcomes feasible? (Phases 1 and 2)

Main research question for a future full trial: Is a narrative SMS intervention with embedded BCTs, with or without an endowment incentive, effective and cost-effective in supporting weight loss and weight loss maintenance at 12 months in obese men compared to a waiting list control?

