- v) Informing the participant of group allocation: The researcher will inform the participant which trial group they are allocated to after randomisation and ensure that they understand what will happen next. An additional specific information sheet will be provided for all three intervention groups, and discussed in detail with the participant. The participant will be given a login by TCTU and will have an opportunity to access the website with the researcher present, to ensure that there are no operational problems. If there is no internet access, the researcher will have screenshots of the website available. The researcher will answer any further questions.
- vi) Future appointment preferences: The researcher will ask what the participants preferred venue, day and time for future appointments are. Target dates for future appointments will be provided. For all groups, the researcher will inform the participant that they will be in contact to arrange the appointment approximately one month in advance of these dates.
- vii) Control group additions: Waiting list control group participants will be offered an alternative version of the SMS intervention. To account for possible dropout and lack of update, additional men will be recruited until 30 35 obese men are allocated to receive the alternative text messages. Additional men will be recruited using the same methods already approved which we have demonstrated to be acceptable and efficient. They will receive a revised information sheet to explain the text only intervention and follow-up assessments at 3 months and a revised consent form which includes consent to contact in future for longer term follow up.

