The front page of the study website will be accessible to all participants. It includes essential information about the trial and links to existing on-line resources e.g. The NHS choices website: http://www.nhs.uk/LiveWell/Loseweight/Pages/Loseweighthome.aspx; and ManvFat: https://manvfat.com/;

The SMS only group web page will have a brief biography and images of the fictional characters featured in the narrative SMS and information specific to this trial arm. There will be also be a link for self-monitoring weight, waist circumference and pedometer steps. Our PPI work to date suggests practical and affordable measurement aids such as notches on belts, a piece of string with felt pen mark, and/or a tape measure.

The SMS with incentives group web page will have access to the same information as the SMS only group. It will also have an additional page about the financial incentives and progress towards weight loss targets.

The SMS waiting list group (control) will only have access to this front page until they have provided outcome data at 12 months. They will receive alternative SMS for 3 months and, similar to the original intervention groups will receive weight loss targets for 3, 6 and 12 months, get access to the webpage information sources and the self-monitoring tools and a pedometer.

WHAT-Procedures: All participants will receive automatic SMS according to the algorithm and SMS library. Men will be encouraged to set ambitious weight loss targets to start with of: 5% of body weight lost at 3 months, 10% at 6 months and 10% at 12 months after the start of the study. These will be personalised and identical to those in the SMS with incentive group. At the 3, 6 and 12 month weighing appointments, men will have the choice of continuing with these weight loss targets of 5%, 10% and 10% or setting lower targets of 5% of body weight at 6 months and 5% at 12 months.

WHO PROVIDES, HOW AND WHERE: The SMS will be delivered by HIC using existing tried and tested automated technology linked to Tayside Clinical Trials Unit currently used in other RCTs. Men will require a standard mobile phone (any type) to maximise reach.

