## **CONTROL GROUP**

Waiting list for SMS intervention: At the 12 month outcome assessment men will be offered an alternative SMS intervention for 3 months, based on the feedback received from intervention men at 3 months and qualitative interview data. At baseline, men will receive information (web or print) about weight loss and a pedometer. There will be no interim measurements or contacts by the research team. Men are therefore free to choose whether to try to lose weight or to self-monitor during the 12 months. They will not have access to the self-monitoring page on the study website until after the 12 month outcome assessment. The NIHR commissioning brief 14/185 asks for non-provision/usual practice. The control arm is as close as possible to "doing nothing", whilst remaining ethical (information, free choice to lose weight and later assistance via SMS to reduce disappointment bias). Men will be asked about their weight and any efforts they have made to change between enrolment and the 12 month assessment, and those choosing to receive alternative text messages will be followed up in person after 3 months using the same procedures as employed during the 3 months follow up of intervention participants.

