## 4.9. SAMPLE SIZE

Feasibility RCT: We aim to randomise 105 men, 35 to each arm, in line with recent recommendations for pilot trials as sufficient to estimate key parameters for a full trial. We will conduct 18-30 face to face or telephone interviews (6-8 men from each trial group) recruited throughout the trial. This sample size is based on previous experience of conducting feasibility studies like this. A sampling frame will ensure diversity for socio-demographic and personal weight loss histories.

Mixed methods process evaluation: All men (n=105) who attend the 12 month assessment will be asked an open question for any suggestions for improving the study. Men who do not attend will be sent a final "thank you" letter informing them of how they can access the findings, and will be invited to provide feedback. Based on previous research experience of applying qualitative research in feasibility RCTs, 18-30 qualitative semi-structured interviews, with a diverse and information rich sample (6-10 from each trial group) are likely to be required to reach data saturation for key themes and for no new thematic issues to arise in interviews. However, some flexibility in the precise sample size is required, as it is impossible to predict important research questions that might arise in a complex intervention study like this. The PhD student will also conduct an additional 18-30 semi-structured interviews to investigate variation in engagement of men and to find out about their experiences after the intervention has finished.

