## 4.10. THE ANALYSIS PLAN FOR THIS STUDY

Given the feasibility nature of the study, the data reported will mainly be descriptive. Summaries of quantitative outcome measures (all time points) will be tabulated by intervention group, including means and standard deviations for continuous variables e.g. weight loss (or medians and interquartile ranges if data are skewed), and proportions for any dichotomous or categorical data. The proportion of individuals contacted who were recruited and the proportion retained in the study at various time-points by group will be determined. Unadjusted mean differences and risk ratios will be calculated for 12 month outcomes to determine evidence of

potential effect of the interventions to test progression criteria, but no further estimates of effect size will be modelled. Completion rates will be reported so that the feasibility of each outcome measure can be assessed. A sample size calculation for a full trial will be performed, incorporating the standard deviation and response rates for the primary outcome. The proportions of participants who ask to stop the texts, withdraw from the study and attend the 3 month assessments will be compared for the original and alternative text messages.

Health Economics: The feasibility of measuring cost and outcomes for the cost-effectiveness analysis in the full trial will be explored. In a future full trial, cost-effectiveness of the interventions will be measured as a cost per Quality Adjusted Life Year (QALY) from an NHS perspective. The resources associated with the interventions will be abstracted from study forms. Other NHS resource use will be collected from participant questionnaires. Resource use estimates will be combined with unit costs obtained from standard sources or study specific estimates. QALYs will be derived from the responses to the EQ-5D. The incremental cost effectiveness ratio (ICER) will be estimated by dividing the difference in mean total costs between the intervention and control group by the difference in QALYs. Bootstrapping will be used to estimate variability in the ICER. A Value of Information analysis will be done to give an indication of the optimal sample size of a future trial.

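### The comparison of original with alternative texts sets men counted from randomisation against 12-month control completers who chose texts plus non-randomised recruits, so a retention difference can appear with identical texts

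*Protocol*

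**What the plan says.** Section 4.10 of the protocol specifies one comparison between text styles: the proportions who ask to stop the texts, withdraw and "attend the 3 month assessments will be compared for the original and alternative text messages". It sets no restriction, adjustment or split by source. Main research question 3 (section 3) gives the purpose: whether the alternative texts are "more acceptable and likely to improve trial retention at 3 months than the existing text message intervention".

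The groups are formed as follows.

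- **Original texts.** Section 4.9: "We aim to randomise 105 men, 35 to each arm". Both intervention arms receive these texts from the start, so the comparator is 35 or 70 men. Section 4.10 does not say which.
- **Alternative texts, ex-control men.** Under section 4.3, control men "will only have access to this front page until they have provided outcome data at 12 months". The alternative texts are offered at that 12-month assessment, and "those choosing to receive alternative text messages will be followed up in person after 3 months".
- **Alternative texts, new men.** The lay summary says "Drop-outs from the control group at 12 months will be replaced through recruiting further men" until at least 30 men receive the alternative texts; section 4.2 vii gives 30 to 35. Of these additional men it says: "They will receive a revised information sheet to explain the text only intervention and follow-up assessments at 3 months".

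**The concern.** The outcome being compared is retention, and part of one group has already been selected on retention. Control men who leave before 12 months, or who attend and decline the texts, never enter the alternative-text denominator; further men are recruited in their place. An original-text man who leaves in week two stays in his denominator. The new recruits avoid the 12-month filter, but they accepted a known text-only offer with a 3-month follow-up, whereas the original-text men accepted randomisation into a 12-month trial. The groups also differ in calendar time and, for ex-controls, in stage of participation.

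A difference could therefore be credited to text style when it comes from how the groups were assembled. Question 3 asks for a comparative answer, and text style is one of the things the study is meant to refine, so a misread difference could influence the design of a later trial.

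**Working it through.** **Inputs from the protocol.** 35 men per arm (3 x 35 = 105, as stated); at least 72% with 12-month outcomes per group (progression criterion 3); an alternative-text group of 30, or 30 to 35. The protocol gives no target difference or precision for this comparison, so there is no stated figure to reproduce.

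**Assumptions, not in the protocol.** Uptake of the texts among control completers is 40% to 100%. A fresh recruit attends the 3-month visit with probability 80% on either text, so there is no text effect. Attendance propensity varies between men on the logit scale with SD 1 to 3.

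**Step 1: composition of the alternative-text group.** Control completers = 35 x 0.72 = 25.2. Their share of 30 men is 25.2 x uptake / 30.

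| Uptake | Ex-controls | Share of 30 | Share of 35 |
|---|---|---|---|
| 100% | 25.2 | 84% | 72% |
| 80% | 20.2 | 67% | 58% |
| 60% | 15.1 | 50% | 43% |
| 40% | 10.1 | 34% | 29% |

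**Step 2: survivor selection alone.** Let P3 and P12 be a man's probabilities of attending the 3-month text visit and the 12-month visit, with intercepts set so that the averages are 0.80 and 0.72. Among 12-month completers, attendance at the text visit is E[P3 x P12] / E[P12]. With k ex-controls and 30 - k new men, combined attendance is [k x completer rate + (30 - k) x 0.80] / 30. Gains below are against 80% for the original texts.

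| SD | Completers attend | Gain, k = 25 | k = 20 | k = 15 | k = 10 |
|---|---|---|---|---|---|
| 1 | 83.6% | +3.0 | +2.4 | +1.8 | +1.2 |
| 1.5 | 86.3% | +5.3 | +4.2 | +3.2 | +2.1 |
| 2 | 88.8% | +7.3 | +5.9 | +4.4 | +2.9 |
| 3 | 92.4% | +10.4 | +8.3 | +6.2 | +4.1 |

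The spurious gain is about 1 to 10 points. A different model, with two classes of men (likely stayers and likely leavers) calibrated to 72% at 12 months, gives about +2 to +13 points at 60-100% uptake.

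**Step 3: allowing for when ex-controls are seen.** Their 3-month text visit falls at 12 + 3 = 15 months after enrolment. Step 2 gives that visit the same 80% average as a newcomer's month-3 visit, which may be too high. Replacing 0.80 by 0.72 or 0.68 for the ex-controls only, with k = 25:

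| SD | Completers (72%) | Bias | Completers (68%) | Bias |
|---|---|---|---|---|
| 1 | 76.3% | -3.1 | 72.6% | -6.2 |
| 1.5 | 79.5% | -0.4 | 75.9% | -3.4 |
| 2 | 82.4% | +2.0 | 78.9% | -0.9 |
| 3 | 86.6% | +5.5 | 83.2% | +2.6 |

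The bias now runs from about -6 to +6 points, so its sign depends on an assumption that the protocol cannot settle.

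**Step 4: random error.** The 95% half-width at 80% attendance is 1.96 x sqrt(0.16/n1 + 0.16/n2).

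- 30 v 35 men: 19.5 points
- 30 v 70 men: 17.1 points
- 10 v 35 men: 28.1 points
- 5 v 35 men: 37.5 points

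**The case against.** The strongest reply is that little depends on this comparison. Section 4.10 calls the analysis mainly descriptive, attaches no test or threshold to this contrast, and none of the six progression criteria uses it. Question 3 also covers acceptability, which has other evidence: feedback from all alternative-text men, 10 to 16 in-depth interviews, and showing men sample texts from the style they did not receive. The bias lies within the random error, and splitting a table by source is something a statistical analysis plan could carry. All of this limits the severity. It does not remove the problem: the protocol itself fixes both the composition of the groups and the contrast, and describing a confounded difference does not make it interpretable.

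A reader might infer three stronger things that the protocol does not support.

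- **That the bias can only favour the alternative texts.** This holds for survivor selection taken alone. Ex-controls are seen after the trial's 12-month endpoint; the £20 reimbursement is tied to the 12-month visit and none is stated for the extra one. If the SMS plus incentive arm is in the comparator, those men have £50 at stake at their 3-month weighing, which could raise original-text attendance.
- **That ex-controls must be the majority.** Uptake is not given. At 72% retention they exceed half of 30 men only if uptake is above about 60%.
- **That the better-retaining style will be adopted in the full trial.** No rule in the protocol says so.

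**Conclusion.** The point stands as a matter that should be fixed. As specified, the contrast mixes text style with selection on earlier attendance, choice of the texts, consent terms and timing, so it cannot show that the alternative texts improve 3-month retention. The upward component from survivor selection is about 1 to 10 points under the step 2 assumptions. The net bias could be of either sign, about -6 to +6 points if ex-controls' marginal attendance is 68-72%. These ranges rest on assumed uptake, attendance and between-man variation, and illustrate size; they do not predict the result. Random error of 17-20 points is a further reason not to read a difference as a text effect. The decision to proceed to a full trial is not directly affected.

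**What to change.** Amend section 4.10 as follows.

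1. Report stop requests, withdrawals and 3-month attendance separately for ex-control men and newly recruited men.
2. For ex-controls, also report uptake and 3-month attendance out of all 35 randomised controls, so that men who dropped out or declined remain visible.
3. Name the original-text comparator. Use the SMS-only arm as the main one, because the alternative texts carry no incentive, and show the SMS plus incentive arm separately.
4. Show new recruits against original-text men over the first 3 months from enrolment, with a confidence interval, as the closer but still non-randomised comparison.
5. State that the comparison is non-randomised and that the ex-control figure is not evidence that the texts improve retention.

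The cost is a few lines and one extra table split, with no new data. The downside is an openly imprecise answer to question 3: with 5 to 10 new men the half-width against 35 is about 28 to 37 points.

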## 4.11. THE ANALYSIS PLAN FOR THE MAIN TRIAL

If the feasibility study is successful, a full trial protocol will include a detailed statistical analysis plan (as per SPIRIT guidelines) which will specify the broad approach for main effects e.g. intention to treat analysis using generalised linear models. The analysis plan will also prespecify subgroup and sensitivity analyses, outline a strategy for dealing with missing data (e.g. multiple imputation) and describe methods for mediation analysis (e.g. using structural equation modelling). Methods for analysing linked data will be determined once the results of the feasibility study are known.

## 5. ETHICAL ARRANGEMENTS

This is a low risk study, where participants could gain benefit to their own health through losing weight and gain financial benefit if they are randomised to the incentive group. The University of Stirling research ethics approval was granted on 8th January 2016 for Phase 1 of this study (June- December 2016) as no NHS sites or patients were involved. The approved protocol is available here: http://www.nets.nihr.ac.uk/projects/phr/1418509.

The main ethical issues are:

1. Ensuring that the incentives are benefiting the health of the individual and the wider public, in terms of the new knowledge that will be generated about how to engage men in weight loss activities, initiate and maintain weight loss. We aim to recruit men in difficult life situations, who do not have many opportunities and who often do not engage in health promoting activities. In

particular, ensuring that the information leaflet promotes the equipoise essential for a randomised controlled trial and minimises disappointment bias. For this reason the amounts of the incentives will not be disclosed in the information leaflet and will only be revealed after randomisation to the incentive arm. Our PPI and 3rd sector stakeholders will have helped us with this. Every effort will be made to ensure that the incentives are not unduly persuasive or coercive.

- 2. Safeguarding for research participants is important. This is a low risk study, however there is a possibility that men who are unsuccessful in their weight loss attempts may become upset and this could impact on their emotional well-being. The researchers will be sensitive to this. In very rare circumstances, if the safety of the participant or of another person was thought to be at risk, the researcher would breach confidentiality. For example if a man told a researcher that he felt suicidal. Under these circumstances, the researcher would speak to the study leads or a senior member of staff in the host institution as soon as possible and in discussion with the participant the next steps would be agreed. The co-chief investigator, [name], is a GP and is therefore trained to manage such situations. Patient information leaflets (web or print) and SMS information which will provide local and national contacts where men can access additional support can be provided. The Health Informatics Centre in Dundee have experience of automatically screening incoming text messages in similar studies for words like suicide, die, and death. The study will use these tried and tested procedures. If a worrying SMS message is identified, the researchers will discuss this with a senior colleague and a plan would be agreed, which may or may not involve alerting appropriate services, following on a risk assessment.
- 3. Safeguarding the safety of researchers is also important. The researchers may work in pairs when recruiting or work alone, according to the neighbourhood and as advised by stakeholders with local knowledge. The Lone Worker Policy for staff working at the University of Stirling will be followed which includes informing a member of staff where and when research tasks are being carried out in the community, contact details and agreed report back times.
- 4. Informed consent. We will adhere to the principles of the Declaration of Helsinki, the HRA guidance (http://www.hra.nhs.uk/). Research Governance procedures according to the University of Stirling will be adhered to: http://www.stir.ac.uk/research/integritygovernanceethics/ and NHS Site approvals will be in place before any NHS patients are recruited. The team have conducted research on financial incentives previously and are aware of the importance of avoiding perceived coercion, bribery and offering an ethical control arm which allows freedom of choice regarding weight loss. Men's Health Forum and our PPI group have chosen the study short name, helped us draft patient information leaflets, the text messages and the website design.
- 5. Data protection. Participant data, contact information and responses to text messages will all be managed and securely electronically in the Participant Tracker Software at the Health Informatics Centre, University of Dundee which is an approved safe haven. Data handling and storage will comply with the Data Protection Act 2003. Researchers employed by the University of Stirling on this study will have will have secure passwords to access the Participant Tracker system at the University of Dundee. Researchers will have undertaken Good Clinical Practice training. Confidentiality will be assured for all data collected. Data from qualitative interviews will be anonymised by removing any information which could potentially identify the participant. Only professional transcribers who are approved by the University of Stirling and meet confidential data handling requirements will be used. Each participant will have a unique ID. The interview recordings, transcriptions and NVivo database will be stored securely in the University of Stirling BOX system, which is password protected and encrypted. The recorder will be wiped clean as soon as the recording has been successfully uploaded to the BOX system. Personal data and audio recordings will be destroyed as soon as it is certain that they are no longer required (i.e. at the end of the study/follow-up period)

